Describe the population to whom the study findings will be generalized

Active duty and DoD beneficiaries aged 30 years or older undergoing cataract surgery
Corneal astigmatism ≥ 1.0 D and a surgical plan that includes a toric intraocular lens for astigmatism correction.

9.6 Benefit to the DoD:

State how this study will impact or be of benefit to the Department of Defense

Uncorrected visual acuity affects warfighter capability to function in combat. Improving uncorrected visual acuity is a goal of military eye care, as evidenced by the robust military refractive surgery program and use of premium intraocular lenses, including toric lenses, at military treatment facilities. Although few active duty members require cataract surgery, those who do may benefit from the outcomes of this study in improving astigmatism correction. Improved visual outcomes in military retirees will also benefit readiness, as many former military members remain in the Inactive Ready Reserves, serve in the Reserves or National Guard, work as contractors on deployed locations overseas, or serve as mentors, leaders, and ambassadors in the community to serve military needs and mission requirements.

10.0

Study Procedures, Data Management, and Privacy

10.1 Study Procedures:

Describe step-by-step how the study will be conducted from beginning to end

The study is a prospective, subject-blinded investigation of whether implanting capsular tension rings with intraocular lenses affects rotational stability of the lens. Male and female Active Duty and DoD beneficiaries who satisfy the inclusion/exclusion criteria will be offered an opportunity to participate. They will be recruited from the ophthalmology clinic located at the Mike O'Callaghan Military Medical Center, 99MDG with prior verbal or written authorization from the patient, the attending physician will refer the patient to the Research Team to obtain more detailed information concerning the study. No research-related procedures will be implemented without the subject first signing an Informed Consent and HIPAA Authorization Document. Each eye will

be assigned a unique study code via a random number generator called the Subject Identification code (001, 002, 003, etc) and randomized independently to the treatment or control group. All of the below items are research-related unless marked as 'standard of care':

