This study has been identified as a significant risk device under a Food and Drug Administration (FDA) approved Investigational Device Exemption (#G190139).

Preoperative Screening:

- Obtained Informed Consent and HIPAA Authorization.
- Record the date of birth, age, gender, race, ethnicity, DoD ID number, phone number(s) and e-mail addresses (used for scheduling). (standard of care)
- Review ocular exam and ocular history to verify the Enrollment Criteria. This will include review of previous ophthalmology encounters, ocular history, ocular exam, refractive error, and corneal astigmatism. (standard of care)
- Potential subjects will be fully informed of the risks of the study. They will be clearly informed that the study requires dilation at postoperative visits, which adds about 30 minutes to the duration of the visit.

One additional note on the number of visits described in this study: The ICD states that the subject may have seven outpatient visits for the study, yet five outpatient visits are described in the Protocol and ICD. This is because patients with both eyes enrolled will require visits on Postoperative Day #1 and Postoperative Week #1 for each eye. That is, the first eye will be checked on Postoperative Day #1 and Postoperative Week #1, then the patient will undergo surgery for the second eye. There will then be an additional five postoperative visits after the second eye has surgery (Postoperative Day #1, Postoperative Week #1, Postoperative Month #1, Postoperative Month #3, and Postoperative Month #6). Please see the lists below for clarification. Patient with one eye enrolled will attend:

- Postoperative Day #1 visit
- Postoperative Week #1
- Postoperative Month #1
- Postoperative Month #3
- Postoperative Month #6

Patient with both eyes enrolled will attend:

- Surgery for the first eye
- Postoperative Day #1 visit for the first eye
- Postoperative Week #1 visit for the first eye
- Surgery for the second eye
- Postoperative Day #1 visit for the second eye
- Postoperative Week #1 visit for the second eye
- Postoperative Month #1 visit for both eyes
- Postoperative Month #3 visit for both eyes
- Postoperative Month #6 visit for both eyes

Criteria for Enrollment of one or both eyes:

- Criteria will be applied to each eye individually in order to determine if one or both eyes may be enrolled in the study.
- Patients will be permitted to enroll both eyes only if both eyes meet all criteria.

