For example, if only one eye meets criteria (for example, one eye has a surgical plan that includes a toric IOL and the other eye doesn't), then only one eye will be enrolled in the study. However, if the fellow eye also meets criteria, then both eyes will be enrolled in the study.

Lens Selection: The patients will undergo standard of care preoperative measurements and planning. The surgeon will evaluate preoperative measurements and use lens calculations, as well as a discussion with the patient, to identify whether a toric lens will be used and to determine the IOL power, cylinder, and target axis (standard of care). Preoperative measurements will be taken using IOL-Master 700, with the addition of the Pentacam and automatic keratometry as needed (standard of care). The toric lens used will be either Tecnis toric II or the Tecnis Eyhance Toric II intraocular lens (Johnson & Johnson Vision). The surgeon, in conjunction with a thorough discussion with the patient, will decide whether to use the Tecnis Toric II or the Tecnis Eyhance Toric II lens based on the patient's pre-existing ocular conditions (prior corneal refractive surgery, irregular corneal astigmatism, severe corneal dystrophy, macular disease, optic atrophy, etc.), refractive goals, lens status of the other eye, and other preoperative factors. All lenses will be used on label (standard of care).

Capsular Tension Ring Selection: The capsular tension rings used in this study will be the MORCHER® EYEJET® CTR Types 14, 14A, and 14C. MORCHER® EYEJET® CTR is a preloaded single-use injector plus capsular tension ring. It is available in two variations: for implantation clockwise (right), and for implantation counterclockwise (left). The clockwise (right) variation will be used in this study.

As recommended by the MORCHER® Instructions for Use, the anatomy of the eye, specifically the bulbous (axial) length, will be taken into account in the selection of the proper CTR size. CTR model 14C is 13.0mm in overall diameter and has a compressed diameter of 11 mm. It is intended for implantation in eyes with axial length of 24-28 mm. CTR model 14 is 12.3 mm in overall diameter and compresses to 10.0 mm. It is intended for implantation in eyes with axial length less than 28 mm. CTR model 14A is 14.5 mm in overall diameter and compresses to 12.0 mm. It is intended for implantation in eyes with bulbous length greater than 28 mm.

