11.0 Statistical/Data Analysis Plan

11.1 Statistical Considerations:

List the statistical methods to be used to address the primary and secondary objectives, specific aims, and/or research hypotheses. Explain how missing data and outliers will be handled in the analysis. The analysis plan should be consistent with the study objectives. Include any subgroup analyses (e.g., gender or age group). Specify statistical methods and variables for each analysis. Describe how confounding variables will be controlled in the data analysis

The primary outcome and dependent variable will be the degree of toric rotation away from the target axis, and the time point of primary endpoint analysis will be when data for the last repeated measurement at 6 months has been obtained. The main treatment effect is a control group receiving a toric IOL only (Group 1) and a treatment group receiving a toric IOL plus capsular tension ring (Group 2). The statistical null hypotheses is as follows:

H01 — there is no difference in means of the degree of toric rotation away from the target axis between control and treatment groups

Subjects will be a random sample of left or right eyes of male and female patients seen in one Air Force medical treatment facility. The patients are presumed to be randomly selected from the population of patients obtaining similar care at this and other Air Force medical treatment facilities.

The study is organized as a mixed effects, randomized design. Subject (eye) is a random effect, as the patients whose eyes are the subjects of this study are presumed to have been randomly elected to obtain this treatment from the population of patients obtaining similar care at these Air Force medical treatment facilities, and the eyes are randomly assigned to treatment or control groups. Treatment is a fixed effect, as the effect of the intraocular lens and capsular tension ring cannot be generalized to other brands of toric intraocular lens or capsular tension rings.

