Reference 5 states eyes treated with a CTR rotated a mean 1.85°(1.72 SD) and eyes without a CTR rotated a mean 4.02°(2.04 SD). The minimum clinically significant difference of toric rotation away from the target axis the researchers wish to detect in this study is 1.85°. Using these parameters, a priori power for a repeated measures n analysis of variance (rANOVA) was assessed using G*Power Version 3.1.9.3. (12). The results indicate 50 subjects (eyes) will have a power of 0.957 at $\alpha = 0.05$ to detect this minimum clinically significant difference between the treatment groups.

Total sample and treatment group means, standard deviations, medians, interquartile ranges (IQR) and ranges will be calculated for interval variables. Frequency distributions will be produced for nominal and ordinal variables. Visual acuity, toric power, intended toric axis, and other variables will be included in the analysis.

The null hypothesis, H01, will be tested by a mixed effects repeated measures analysis of variance (rANOVA) using a general linear model, $y_{ij} = \mu + \alpha_i + \beta_j + \gamma_{ij} + \epsilon_{ij}$, where μ is the main treatment effect, α_i is time of repeated measure, and β_j represents the influence of individual j on his/her repeated observations.

[name], Senior Research Biostatistician Subject Matter Expert for Clinical Research Management under contracts OMNI 0004 3-82 and OMNI 0005 3-126, is the statistical consultant supporting this study. Statistical analysis will be performed with R Version 3.5.1. (13)

11.2 Sample Size:

50 eyes (approximately 25 eyes in each group) -- We are enrolling by number of eyes. If subjects have one eye that meets enrollment criteria, then that eye will be randomized into the treatment or control group. If both eyes meet enrollment criteria, then each eye will be randomized independently.

11.3 Total number of subjects requested (including records and specimens):

50

11.4 If you are recruiting by study arm, please identify the arms of the study and how many subjects will be enrolled in each arm

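### Fellow eyes enter the trial and are randomised separately, but the primary model has no patient level to link them

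*Combined protocol and SAP*

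**What the plan says.** Section 10.1 applies eligibility eye by eye and states that "if the fellow eye also meets criteria, then both eyes will be enrolled in the study". It gives bilateral patients their own visit schedule. Sections 10.1, 11.2 and 11.4 set the allocation rule: "If both eyes meet enrollment criteria, then each eye will be randomized independently". Sections 10.1 and 11.4 name the possible results for a bilateral patient: one eye in each arm, both in control, or both in treatment.

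Section 11.2 says "We are enrolling by number of eyes", with a target of 50 eyes and about 25 per arm. The 50 eyes can therefore come from 25 to 50 patients, with 0 to 25 of them bilateral.

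Sections 11.1, 11.5 and 11.6 name one random effect: "Subject (eye) is a random effect". The model in 11.1 and 11.6 has one subject-level term, described there as the influence of the individual on his or her own repeated observations. No patient random effect, clustered standard error or paired analysis appears. The power statement is that "50 subjects (eyes) will have a power of 0.957".

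Under 10.1 each eye is to "be assigned a unique study code via a random number generator called the Subject Identification code". Under 10.2 only coded data go to analysis. Section 10.14 keeps an identifiable master key but does not say that a patient-level code reaches the analyst.

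**The concern.** Two eyes of one patient may rotate alike. Section 9.2 names axial length and lens material among the factors that affect rotation, and section 10.1 makes lens choice depend partly on the lens status of the other eye. A positive correlation is therefore plausible, though the documents do not give one.

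A model whose only random effect is the eye treats fellow eyes as unrelated. With positive correlation:

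- in a same-arm pair, the second eye adds less information than the model assumes, so the standard error is too small;
- in a split pair, the shared patient effect cancels from the treatment difference, so the standard error is too large and the patient's value as own control is lost.

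Independent randomisation balances the two errors on average. It does not balance them in the one trial that is run, where the mix of pairs is fixed by chance.

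The wording about the individual does not settle the matter. If it means the eye, fellow eyes are unlinked. If it means the patient, visits are no longer grouped within eyes. One term cannot carry both levels.

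**Working it through.** **Inputs from the documents (11.1, 11.2).** SDs 1.72 and 2.04 degrees; difference to detect 1.85 degrees; 50 eyes, about 25 per arm; alpha 0.05; five postoperative visits (10.1).

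**Assumed, not in the documents.** Between-visit correlation 0.82, chosen to reproduce the stated power; a two-sided test; inter-eye correlation r of 0.1, 0.3, 0.5 or 0.7; B = 5, 10 or 25 bilateral patients; complete visits.

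**1. The plan's power.** Pooled SD = sqrt((1.72² + 2.04²)/2) = 1.887. Effect size f = 1.85/(2 × 1.887) = 0.490. For the between-group test, lambda = f² × 50 × 5/(1 + 4 × 0.82) = 14.04 on 1 and 48 df, and power is 0.9565, which matches 0.957. A between-visit correlation of 0.75 gives 0.967 and 0.90 gives 0.943. All of these take the 50 eyes as independent.

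**2. Standard error given the pairs.** With 25 eyes per arm the eye-only variance is 2σ²/25. Each same-arm pair adds 2rσ²/625 and each split pair subtracts it. With D split pairs out of B:

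true/model variance = 1 + 2r(B − 2D)/50

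type I error = 2 × (1 − Φ(1.96/√ratio))

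D follows Binomial(B, 0.5). Its 2.5th and 97.5th percentiles are 0 and 5 (B = 5), 2 and 8 (B = 10), 8 and 17 (B = 25). Example: B = 10, D = 2, r = 0.5 gives ratio 1 + 2 × 0.5 × 6/50 = 1.12 and type I error 6.4%.

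Eye-only type I error (%), few split pairs / many split pairs:

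| B | r = 0.1 | 0.3 | 0.5 | 0.7 |
|---|---|---|---|---|
| 5 | 5.2 / 4.8 | 5.7 / 4.3 | 6.2 / 3.9 | 6.6 / 3.5 |
| 10 | 5.3 / 4.7 | 5.8 / 4.2 | 6.4 / 3.7 | 7.0 / 3.2 |
| 25 | 5.4 / 4.6 | 6.3 / 3.8 | 7.1 / 3.0 | 8.0 / 2.3 |

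At the quartiles of D the departure is milder. Across r = 0.1 to 0.7 it runs from 5.1/4.9 to 5.6/4.4 with B = 10, and from 5.1/4.9 to 6.0/4.1 with B = 25.

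**3. Average over the randomisation.** Simulation (8,000 null and 8,000 alternative trials per setting, on eye means; Monte Carlo standard error about 0.24 points for type I error) gives the eye-only model type I error of 4.7-5.4% and power of 0.948-0.955.

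**4. Two-level model.** With random intercepts for patient and eye and a Kenward-Roger correction, type I error at the same extreme splits is 4.6-5.5% with 10 or 25 bilateral patients and 4.5-5.9% with 5. At r = 0.5, simulated eye-only and then corrected two-level error are:

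- B = 10: D = 2, 6.8% and 5.3%; D = 8, 3.8% and 5.1%.
- B = 25: D = 8, 7.1% and 5.2%; D = 17, 3.0% and 4.8%.

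Without the correction, a Wald test of the two-level model has type I error of 5.9-9.7%.

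**5. Information lost.** Excess variance of the eye-only estimate over generalised least squares with r known (an upper bound on the gain), and simulated power from eye-only to two-level:

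| B | Excess variance, r = 0.1 / 0.3 / 0.5 / 0.7 | Power, r = 0.3 | Power, r = 0.5 | Power, r = 0.7 |
|---|---|---|---|---|
| 5 | 0.2 / 2 / 6 / 18% | 0.953 to 0.946 | 0.950 to 0.950 | 0.954 to 0.965 |
| 10 | 0.4 / 4 / 13 / about 36-37% | 0.950 to 0.948 | 0.951 to 0.961 | 0.948 to 0.979 |
| 25 | 1 / 10 / 32 / 92% | 0.953 to 0.960 | 0.950 to 0.982 | 0.954 to 0.997 |

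At r = 0.1 power does not improve for any B.

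**The case against.** The strongest reply is that the planned test is valid by the usual standard: over the randomisation its type I error is about 5% and its power is as stated. On this view, asking for calibration given the number of split pairs is a choice, and better use of those pairs is an improvement, not a repair. This stands as a limit on the claim. But only one trial is run, the number of split pairs carries no information about the treatment effect, and a standard error known not to fit the observed pairs is hard to defend.

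The size also rests on unstated inputs. Eligibility is judged per eye, and the protocol's own example is a patient with one eligible eye, so bilateral patients may be few. The largest figures need every patient to be bilateral and a correlation of 0.7. With 5 bilateral patients the percentiles used are the most extreme splits possible. At 10 bilateral patients and r = 0.5 the quartiles give only 5.5% and 4.5%, and the power gain is one point. The cited CTR-group SD (1.72) is close to its mean (1.85), which suggests skewed data, and the figures here were not checked against skewness. All of this stands: the omission is certain, its consequence is not.

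Finally, coded data are not unlinkable data, and a master key exists. That is fair. The identifier is a detail to write down and does not carry the argument.

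**Conclusion.** The concern holds. The analysis as written does not handle fellow eyes that the protocol expects to enrol, on either reading of the subject term. The defect lies in the standard error for the realised mix of pairs and in the unused within-patient contrast. Average type I error and the stated power are not at fault.

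The effect is negligible with few bilateral patients or an inter-eye correlation near 0.1. It becomes material from about 10 bilateral patients and a correlation of 0.5, and even there mainly when the split is unbalanced. These thresholds depend on the assumed correlations and numbers of bilateral patients, on complete visits, and, for the corrected two-level model, on simulation. The point should be fixed, because the mix of pairs is unknown until enrolment ends and a model chosen after seeing it would be open to challenge.

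**What to change.** - In 11.1 and 11.6, specify random intercepts for patient and for eye within patient, with a Kenward-Roger type small-sample correction. The correction is essential, given the liberal uncorrected Wald test.
- State that the subject term in the model equation means the eye nested in the patient.
- State that the analysis file carries a coded patient identifier shared by both eyes, derived from the master key.
- Report the numbers of patients, bilateral patients and split-arm pairs.
- State in 11.1, 11.5 and 11.6 that the power of 0.957 assumes 50 independent eyes.

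The cost is small: wording, one coded identifier and one more variance component, with no extra visits and no change to the 50 eyes. There are two drawbacks. The patient variance will sometimes be estimated as zero (32-41% of null trials at correlation 0.1, 7-25% at 0.3, 1-11% at 0.5). Power falls by about one percentage point at worst (0.955 to 0.943 with 5 bilateral patients and no correlation). With few bilateral patients or low correlation, the gain is in calibration at most, not in power.

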Randomization: Each eye undergoing cataract surgery will be randomized into a control or treatment group. If both eyes meet enrollment criteria, then each eye will be randomized independently. For patients able to enroll both eyes into the study, potential outcomes could be: a. one eye could be randomized into the control group and one eye could be randomized into the treatment group, b) both eyes could be randomized into the control group, or c) both eyes could be randomized into the treatment group.

- Control group: toric IOL only
- Treatment group: toric IOL plus capsular tension ring

Assignment of the eye to the control or treatment group will be revealed during the cataract surgery at the point of potential capsular tension ring insertion. The surgeon and clinical staff (ophthalmic technicians and nurses) will not know whether the eye is in the treatment/control group until after the cataract has been removed and it is time for potential capsular tension ring placement. The eye will have been previously assigned to the control or treatment group using a random number generator by clinical research personnel, who are not involved in patient care. The group assignment will be documented in an opaque, sealed envelope, which will be present in the operating room at the time of surgery. The envelope will be opened by operating room staff after lens removal, and the surgeon will be informed. If the capsular tension ring is to be implanted, the correct size will be selected and verified, then implanted.

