12.4 Special categories, check all that apply

Minors /Children
 Students
 Employees - Civilian
 Employees - Contractor
 Resident/trainee
 Cadets /Midshipmen
 Active Duty Military Personnel
 Wounded Warriors
 Economically Disadvantaged Persons
 Educationally Disadvantaged Persons
 Physically Challenged (Physical challenges include visual and/or auditory impairment)
 Persons with Impaired Decisional Capacity
 Prisoners
 Pregnant Women, Fetuses, and Neonates
 Non-English Speakers
 International Research involving Foreign Nationals - Headquarters Review is necessary

You must also consider the requirements of DoDI 3216.02, Enclosure 3, paragraph 7.e.

12.5 Inclusion Criteria:

Order Number	Criteria
1	
 • Active duty and DoD beneficiaries aged 30 years or older undergoing cataract surgery • Corneal astigmatism = 1.0 D and a surgical plan that includes a toric intraocular lens for astigmatism correction. 
 ◦ The lenses used will be the Tecnis Toric II IOL and the Eyhance Toric II IOL (Johnson & Johnson Vision). The lenses will be used on label. • No observed zonular or capsular problems prior to, or at the time of, capsular tension ring insertion

12.6 Exclusion Criteria:

Order Number	Criteria
	
 • Patients who are pregnant or lactating

1

- Patients undergoing cataract surgery who do not have corneal astigmatism =1.0 D.
- Any observed zonular or capsular problems prior to, or at the time of, capsular tension ring insertion.
- Pre-existing ocular conditions, including:
 - Pseudoexfoliation syndrome in one or both eyes
 - Prior incisional ocular surgery
 - Lens subluxation
 - Poor dilation or inability to position at the slit lamp (making postoperative outcome measurements difficult or impossible)
 - Plans for extensive travel or to move away during the postoperative evaluation period
 - Other conditions that would influence the capsule or lens positioning
- Surgical plan that includes other procedures at the time of initial cataract surgery, such as Limbal Relaxing Incisions (LRIs), Micro-Incisional Glaucoma Surgery (MIGS), etc.
- Legally Authorized Representatives will not be utilized in this study

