Explain the process for withdrawal and specify whether or not the subjects will be given the opportunity to withdraw their data their data/specimens in the event they wish to withdraw from the study

If a participant first agrees to participate and then changes their mind, they are free to withdraw consent and discontinue participation at any time. Their decision will not affect their ability to receive medical care and will not be penalized or lose any benefits to which they would otherwise be entitled. There are no risks from withdrawing. They will be advised in the Informed Consent process that if they decide to withdraw from the study early, we will ask them to discuss their decision with the study staff. The researcher may withdraw them from the study prior to the study's end without their consent for one or more of the following reasons: Failure to follow the instructions of the researchers and study staff. The researcher decides that continuing their participation is not in their best interests. The study is cancelled. Other administrative reasons. Unanticipated circumstances. They become Pregnant or begin lactating. If they lose their status as a military health care beneficiary, they can no longer be included in the study.

Patients will be discontinued from the study if intraoperative complications or concerns are noted PRIOR to capsular tension ring insertion.

Intraoperative complications may include:

- capsular bag tears or rents
- anterior vitrectomy
- phacodonesis
- damaged zonules
- use of non-toric intraocular lens
- other intraoperative complications that would influence capsule or lens positioning or stability

Patients will continue to be enrolled in the study to further characterize the safety of the investigational device and treatment if intraoperative complications occur DURING OR AFTER the point of possible capsular tension ring insertion. This includes secondary surgical interventions such as repositioning of the IOL. These eyes will not be included in the data analysis after this point.

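### Is the stated power of 0.957 undermined because all 50 enrolled eyes must be analysed and some G*Power inputs are missing?

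*Combined protocol and SAP*

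**What the plan says.** Sections 11.1, 11.5 and 11.6 cite a published trial of toric lenses with and without a capsular tension ring (mean rotation 1.85 degrees, SD 1.72, with the ring; 4.02 degrees, SD 2.04, without). They set 1.85 degrees as the smallest difference worth detecting, name a repeated measures ANOVA in G*Power, and conclude: "The results indicate 50 subjects (eyes) will have a power of 0.957" at alpha 0.05. Section 11.2 sets the sample at "50 eyes (approximately 25 eyes in each group"), and section 11.3 requests 50.

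Allocation precedes surgery. Section 11.4 says: "The eye will have been previously assigned to the control or treatment group using a random number generator by clinical research personnel", and the envelope is opened once the lens is out. Section 13.6 then removes eyes at two stages:

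- Before the ring step: "Patients will be discontinued from the study if intraoperative complications or concerns are noted PRIOR to capsular tension ring insertion".
- During or after the ring step, the patient stays in follow-up for safety. "This includes secondary surgical interventions such as repositioning of the IOL", and "These eyes will not be included in the data analysis after this point".

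Section 13.6 also allows withdrawal by the patient or the investigator, and adds: "If they lose their status as a military health care beneficiary, they can no longer be included in the study". Section 12.5 lists among the inclusion criteria: "No observed zonular or capsular problems prior to, or at the time of, capsular tension ring insertion". Under the missed-visits heading in section 10.1, subjects who miss visits stay in the study and are recalled up to day 210.

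**The concern.** The number powered and the number enrolled are both 50, so 0.957 holds in full only if every enrolled eye contributes outcome data. Yet the plan's own rules remove eyes that have already been allocated, with no inflation for loss and no statement on whether an eye discontinued before the ring step counts towards the 50 or is replaced.

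A reader also cannot rerun the calculation. Power for a between-group effect in a repeated measures ANOVA depends on the SD, the number of measurements and the correlation among them. The plan does not say which values were entered.

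This is the trial's only justification of size. If the figure were materially too high, the stated 4.3% chance of missing a true difference of 1.85 degrees (1 - 0.957) would be too low, and a null result would look firmer than it is.

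**Working it through.** **Inputs from the plan (11.1, 11.2):** N = 50, about 25 per arm; difference 1.85 degrees; SDs 1.72 and 2.04; alpha 0.05; power 0.957. **From section 10.1:** five scheduled postoperative visits (day 1, week 1, months 1, 3 and 6). **Not stated:** the SD entered, the number of measurements m entered, and the within-eye correlation rho.

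**Which test.** H01 in 11.1 is non-directional, the power sentence refers to a difference between the treatment groups, and the F-test for two groups is two-sided. The between-group F-test with 1 and N - 2 degrees of freedom is therefore the natural reading.

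**Step 1: can 0.957 be reached?**

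- Pooled SD = sqrt((1.72² + 2.04²)/2) = 1.887
- d = 1.85/1.887 = 0.980, and f = d/2 = 0.490
- Noncentrality: lambda = f² × N × m / (1 + (m - 1) × rho)

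Solving for power 0.957 at N = 50 gives lambda = 14.08. With f² × N = 12.02, the implied correlations are:

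| Measurements m | rho, SD 1.887 | rho, SD 2.04 |
|---|---|---|
| 2 | 0.71 | 0.46 |
| 3 | 0.78 | 0.60 |
| 4 | 0.80 | 0.64 |
| 5 | 0.82 | 0.66 |

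For SD 1.887 and m = 5, power is 0.992 at rho = 0.5, 0.960 at 0.8 and 0.925 as rho approaches 1. The stated value lies inside this range, at a possible correlation. It is reachable, though not uniquely determined by what is printed.

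**Step 2: eyes that give no outcome data.** Lambda is proportional to N, so lambda × N/50 carries the plan's figure to fewer eyes without needing the missing inputs. The plan states no loss rate, so the losses below are assumptions.

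| Eyes analysed | Eyes lost | Power | Chance of missing 1.85 degrees |
|---|---|---|---|
| 50 | 0 | 0.957 | 4.3% |
| 48 | 2 (4%) | 0.949 | 5.1% |
| 45 | 5 (10%) | 0.936 | 6.4% |
| 42 | 8 (16%) | 0.919 | 8.1% |
| 40 | 10 (20%) | 0.905 | 9.5% |
| 30 | 20 (40%) | 0.801 | 19.9% |

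An uneven split of 40 eyes into 22 and 18 gives 0.902.

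**Step 3: eyes that leave after early visits.** Section 13.6 excludes eyes with later complications or repositioning only from that point on. Under compound symmetry an eye with m visits carries information m/(1 + (m - 1) × rho). With rho = 0.8165:

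- five visits: 5/4.266 = 1.172
- two visits: 2/1.8165 = 1.101, which is 94% of the full amount
- one visit: 1, which is 85%

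If five eyes leave after week 1, lambda = 14.08 × (45 + 5 × 0.939)/50 = 14.00 and power is about 0.956. If ten leave, lambda = 14.08 × (40 + 10 × 0.939)/50 = 13.91 and power is about 0.955. This needs incomplete eyes to stay in the model, which fits a mixed effects analysis with eye as a random effect, though the plan does not spell it out.

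**Step 4: do eyes removed before the ring step use up the 50?** Two readings are open. Section 12.5 makes the absence of zonular or capsular problems up to ring insertion an inclusion criterion, and 11.2 counts eyes that meet the enrolment criteria. On that reading an eye that fails at surgery is ineligible and need not count. Section 13.6 speaks of discontinuing such patients, which suggests that they had been enrolled. Step 2 bounds the effect of the second reading.

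**The case for a change.** The strongest argument for a change is that the figure is the only size justification, that the rules in 13.6 make full analysis of 50 eyes unlikely, and that correction costs a few words. Recall of missed visits cannot bring back an eye that the protocol itself has discontinued. An eye removed before the ring step gives no outcome data at all, so the mitigation in step 3 does not reach it. At 20% loss the chance of missing the target difference would be about twice the stated one (9.5% against 4.3%). Without a replacement rule, staff must also settle case by case whether to enrol a further eye.

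Much of this stands as description. Fifty is both the powered and the enrolled number, no loss allowance appears, and three inputs are missing. What does not stand is the step from there to a wrong figure. The sentence gives power at 50 eyes and is attainable at 50 eyes. A restated value such as 0.94 would rest on a 10% loss that appears nowhere in the documents, and would replace the plan's figure with a guess. The replacement question affects the count of eyes at the margin, and the number of eyes actually analysed will be known when the trial is reported.

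**Conclusion.** No change to the plan follows. The power of 0.957 is attainable by the stated method and nothing in the documents shows it to be wrong. It is best read as the power with 50 analysed eyes. Power is still 0.905 if 10 of 50 eyes yield nothing, falls to about 0.80 only near 40% loss, and hardly moves for eyes that leave after week 1. The choice of 50 eyes therefore survives any moderate loss, and neither the analysis nor its interpretation depends on the third decimal of a planning figure. Once the trial is complete, its precision is read from the estimate and its confidence interval.

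The missing correlation, SD and number of measurements, and the silence on replacement, are gaps in reporting that leave the results unaffected.

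The conclusion rests on four assumptions: the two-sided between-group F-test; eyes treated as independent units, as in that calculation; equal correlation among visits; and losses of 4% to 20% as an illustrative range, since the plan states none. Step 3 further assumes that early visits of incomplete eyes are kept in the model.
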